### 4.4 VISIT 3 (PROCEDURE DAY / MEETING #3)

**Third meeting** - to be performed 1 week after the 1st meeting.

Activities for the meeting are detailed hereafter:

1. **Learning about the application:** Reviewing the manuals of the application, the different options, the logic etc. - ~30 min.
2. **Using the application (with guidance of instructor):** Writing free sentences, using the features of the application, calling for help, going to rest mode etc. - ~1 hour.
3. **Using the full logic of the EyeControl:** ~30 min

The user will be asked to go through the menus and turn on the application, and compose full sentences using the system. *(The tests in this session will focus on the*

*application features. The test will include also the pre-defined sentences and the idea is to show the learning curve when compared to the Second meeting of the pre- defined sentences). The test will include: 5 pre-defined sentences, Opening the application and writing 2-3 Words.*

**Using the Alpha Bet feature / free text:** writing the alphabet without the screen.  
**Writing 2-3 Words-same words as in the application ~1 hour.**

4. Any adverse events will be recorded.

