The camera connects to a small computer, "Odroid", which is connected to a speaker. The computer translates the pupil's movements and gives an audible sound environment. In addition, by broadcasting through Bluetooth, the patient can use various applications on their smart phone to communicate with others. An outstanding benefit is the fact that the calibration of the pupils is automatic process based on an algorithm without the need for outside aid.

The Product is based on an innovative technology that enables the eye to function as a joystick. The product is innovative (being **portable**), significantly cheaper than other products on the market, comfortable (automatic calibration and independence), Mobile (glasses and a tiny small computer), and allows the patient to communicate with the environment anywhere and anytime. **This is a revolution for patients and their surroundings – the possibility to return to social activity regaining independence and the ability to communicate with the environment.**

The solution developed consists of 3 levels: a call for help, choosing from pre-defined phrases (English and Hebrew) and composing sentences using a virtual board with the alphabet encoding. All these can be played over the loudspeaker while the user is able to hear with headset every letter/word/sentence before he chooses\ it, so that the user doesn't need the screen in front of him.

[figure not shown]

Chart 1: The product

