## 1.7 STUDY ENDPOINTS

### Primary endpoint:

Assessment of the feasibility of the use of EyeControl device, measured by:

- **Ability to perform device features:**
  - Controlling the EyeControl's Joystick [measured by successful correct performance of over 70% of the gestures].
  - Controlling the Rest mode and Siren mode [measured by successful correct performance of over 70% of the gestures].
  - Testing the logic of the pre-defined sentences;
    - a. ability to say 10 pre-defined sentences [over 80% success rate];
    - b. Time - perform each sentence in less than 2 minutes – [over 80% success rate for all sentences].
  - Controlling the application and Free text features –words per minute, using the application Alphabet
- **Required Training time/ learning curve of;**
  - pre-defined device features [selected results after the 4th meeting compared with results results of previous meetings]
  - free speech [selected results after the 4th meeting compared with results after the 3rd meeting]
- **Usability** feedback (user experience) questionnaire completed by each user.

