#### 4.5 VISIT 4 (PROCEDURE DAY / MEETING #4)

**Fourth meeting** – to be performed on the same week as meeting #3 (2-3 days later).

1. **Using the full logic of the EyeControl -~1.5 hours**

The user will be asked to go through the menus and turn on the application, and compose full sentences using the device. The user will also be asked to use the application in order to write free text. Finally the user will be asked to write words in the application comparing to the Alpha Bet mode. (The tests will focus on the application features and different than the first test. Now the test will include writing free text in the application. The test will also consist the pre-defined sentences and the idea is showing the learning curve from the last test)- **The test will include: 5 pre-defined sentences, Opening the application and writing 5 Words in the application, writing 5 words in the Alpha Bet mode.**

2. Final Questionnaire – The users will be asked to complete a usability and feedback questionnaire at the end of meeting #4 - ~1 hour.
3. Any adverse events will be recorded.
4. Complete study exit form.

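### Application and screen-free (Alpha Bet) writing are tested in one listed order, with the same words at meeting 3 and no word rule at meeting 4, so the planned mode comparison is confounded in an unknown direction

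*Protocol*

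**What the plan says.** Section 4.4 (meeting 3) begins with about 30 minutes on the application manuals and about 1 hour under "Using the application (with guidance of instructor"). A test block of about 30 minutes follows and includes "Opening the application and writing 2-3 Words". Last comes the Alpha Bet feature, described as "writing the alphabet without the screen", with the task "Writing 2-3 Words-same words as in the application ~1 hour".

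Section 4.5 (meeting 4) says: "Finally the user will be asked to write words in the application comparing to the Alpha Bet mode". Its test content is listed as "Opening the application and writing 5 Words in the application, writing 5 words in the Alpha Bet mode". It does not say whether the two sets of five words are the same.

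Section 1.7 makes free text part of the primary endpoint, measured as "words per minute, using the application Alphabet", with no success threshold. It also names a free-speech learning curve that sets selected meeting 4 results against those of meeting 3. Section 1.3 presents screen-free use as a feature of the device: the user hears each choice through a headset, "so that the user doesn't need the screen in front of him".

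The protocol nowhere alternates or randomises the order of the two writing tests.

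**The concern.** Each subject writes in both modes and the modes are to be compared, so this part of the study works as a within-subject comparison of two conditions. Such a comparison needs either a varied order or a reason to think order does not matter. Here the listed order is the same for all, and at meeting 3 the second test repeats the words of the first.

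Two readings of the results are at stake.

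- **Application against Alpha Bet.** A difference, or the lack of one, could reflect the mode, having just written the words, the point in the session, or the training given beforehand.
- **Meeting 4 against meeting 3.** If Alpha Bet results enter the free-speech learning curve, the meeting 3 value rests on words written earlier in the same session. The meeting 4 value may or may not. Real learning could be hidden or exaggerated.

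This is fixed when the data are collected. No later analysis can recover it.

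**Working it through.** The protocol gives no figure on this point, so there is none to reproduce.

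**Inputs**

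- Up to 10 healthy volunteers and up to 5 ALS patients (section 2).
- Meeting 3: application 2-3 words, then Alpha Bet with the same words (section 4.4).
- Meeting 4: application 5 words, then Alpha Bet 5 words, with no word rule (section 4.5).
- Size of any order or rehearsal effect: not given. Values below are assumptions.

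**Step 1. Can mode and order be separated?** Take a linear model with one effect per subject plus mode and order.

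| Design | Subjects | Parameters | Rank |
|---|---|---|---|
| Fixed order | 10 | 12 | 11 |
| Fixed order | 5 | 7 | 6 |
| Both orders, 5/5 | 10 | 12 | 12 |
| Both orders, 3/2 | 5 | 7 | 7 |

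Under a fixed order the mode and order columns are identical, so more subjects would not help.

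**Step 2. How far could the mode comparison move?** Under the fixed order, observed speed ratio (Alpha Bet / application) = true ratio × order effect. For a true ratio of 0.80:

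- order effect 0.8: 0.80 × 0.8 = 0.64
- order effect 1.0: 0.80 × 1.0 = 0.80
- order effect 1.3: 0.80 × 1.3 = 1.04

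The same true difference could look like a large deficit or a slight advantage.

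**Step 3. Which way does the bias go?** The listed times at meeting 3 are 30 + 60 + 30 + 60 = 180 minutes, so Alpha Bet falls in the last hour. The instruction and guided use before it, 30 + 60 = 90 minutes, centre on the application. Both work against Alpha Bet; repeated words work for it. The net sign cannot be derived from the protocol.

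**Step 4. The learning curve.** Suppose Alpha Bet words are rehearsed at meeting 3 and not at meeting 4. Observed speed ratio (meeting 4 / meeting 3) = true learning ratio / rehearsal factor. If learning cuts writing time by 20%, the true ratio is 1/0.8 = 1.25. Then:

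- rehearsal factor 1.0: 1.25/1.0 = 1.25
- rehearsal factor 1.1: 1.25/1.1 = 1.14
- rehearsal factor 1.25: 1.25/1.25 = 1.00
- rehearsal factor 1.3: 1.25/1.3 = 0.96

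If meeting 4 also repeats words, this distortion largely goes. That is why the missing word rule matters.

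**Step 5. What does varying the order achieve?** Let m be the mode difference, o the order effect, cA the carry-over from application to Alpha Bet, and cB the reverse. The expected difference (Alpha Bet minus application) is m + o + cA in one order and m − o − cB in the other. Their average is m + (cA − cB)/2, so o cancels. A raw mean over all subjects keeps (5 − 5)/10 = 0% of o with a 5/5 split and (3 − 2)/5 = 20% with a 3/2 split; averaging within each order first removes that remainder. Unequal carry-over does not cancel, which is why different words per mode are also needed.

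**The case against.** The strongest reply is that identical words are a sensible control. With only 2-3 words per test, repeating them keeps word difficulty out of the mode contrast. This stands as far as it goes: reuse alone is not the flaw. Combined with one fixed order, it trades an imbalance in difficulty for one in practice.

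Second, the only stated mode comparison is at meeting 4, where word reuse is not stated and the order rests on how the items are listed. The meeting 3 order is firmer, because its Alpha Bet words are defined by the application test. This narrows the point, but a protocol that intends a comparison should fix the order and the word rule.

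Third, the link to the endpoints is limited. Application against Alpha Bet is not a named endpoint. The words-per-minute wording may refer to application writing, which comes first. Whether Alpha Bet enters the learning curve is left open by the reference to selected results. The learning-curve concern is therefore conditional.

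A reader might infer that carry-over inflates screen-free speed, on the ground that subjects recall a gesture sequence they have just practised. The documents do not support that. They do not say the two modes share one gesture coding, they do not give the interval between the tests, and they contain influences that work the other way.

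Finally, this is a small descriptive study without a power claim (section 9). That lowers the severity. It does not make an avoidable bias harmless, because the descriptive numbers are the whole result.

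**Conclusion.** The point holds in a limited form. As listed, application and Alpha Bet writing come in one order for up to 10 + 5 = 15 subjects, and mode is fully aliased with order. The comparison asked for in section 4.5 is confounded with order, practice and fatigue, and the direction is unknown. A learning curve that uses Alpha Bet results may set rehearsed words against unrehearsed ones.

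The aliasing follows from the design and needs no numerical assumption, except that the listed order at meeting 4 is the order followed. The ratios of 0.64 to 1.04 and 0.96 to 1.25 are illustrations on assumed effects, not estimates. Severity is low to moderate: no pass/fail result depends on the contrast and no words-per-minute threshold is set.

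**What to change.** Amend sections 4.4 and 4.5 as follows.

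1. Assign the order of the two writing tests by subject number within each group: odd numbers application first, even numbers Alpha Bet first. Keep each subject's order the same at meetings 3 and 4. Changing it between meetings would add an order change to the learning curve.
2. Prepare two word lists per meeting, matched on number of letters. Rotate which list goes with which mode between subjects, so that list is not tied to mode. Repeat no word within a session, and apply the same rule at both meetings.
3. Report words per minute separately by mode. Compute the mode difference within each order and average the two, which handles a 3/2 split among five patients.
4. State whether the free-speech learning curve uses application results, Alpha Bet results or both.

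The cost is a few lines of text and printed lists, with no added subjects or session time. There are two small downsides: word difficulty is balanced across subjects instead of identical within each, and about half the subjects take the screen-free test before the application test. The change does not remove the unequal training before the tests, so the report should describe the mode difference as one seen after application-centred instruction.

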#### 4.5 VISIT 4 (PROCEDURE DAY / MEETING #4)

**Fourth meeting** – to be performed on the same week as meeting #3 (2-3 days later).

1. **Using the full logic of the EyeControl -~1.5 hours**

The user will be asked to go through the menus and turn on the application, and compose full sentences using the device. The user will also be asked to use the application in order to write free text. Finally the user will be asked to write words in the application comparing to the Alpha Bet mode. (The tests will focus on the application features and different than the first test. Now the test will include writing free text in the application. The test will also consist the pre-defined sentences and the idea is showing the learning curve from the last test)- **The test will include: 5 pre-defined sentences, Opening the application and writing 5 Words in the application, writing 5 words in the Alpha Bet mode.**

2. Final Questionnaire – The users will be asked to complete a usability and feedback questionnaire at the end of meeting #4 - ~1 hour.
3. Any adverse events will be recorded.
4. Complete study exit form.

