	
The overall duration of participation for each subject will be up to 3 weeks.
 
The place: Rambam health care campus.
 
Each subject will go through a series of 4 meetings (2 meetings per week), and up to 3 hours per meeting. Meetings will be accompanied by company representatives and/or trained study team.
 
Procedure will consist of an introduction and demonstration of the device features followed by actual use of the device by each subject (including control of gestures, use of menus, activation of pre-defined modes and writing full sentences). User feedback/questionnaire will be completed after the 2nd and 4th session.
 
The user's ability to perform each of the pre-defined tasks, will be measured in each session. In addition, success rate and measured time for completion of pre-defined tasks, collected after the 4th session, will be compared to the success rate and times collected in previous sessions.

Patient Population:	
The subject population is divided into two groups:
 
 
1. Healthy volunteers- up to 10 subjects
 
2. Early stage ALS patients – up to 5 early stage ALS patients that can still communicate orally.
 

No. of Subjects/Sites:	1 site - Rambam Health Care Campus
Study duration:	
Screening: one day.
 
Procedure: 4 sessions of about 2.5-3 hours for each participant, performed over 2 weeks' time.
 
Follow up: none.

Endpoints	
Primary endpoint:
 
Assessment of the feasibility of the use of EyeControl device, measured by:
 
 
• Ability to perform device features: 
 
○ Controlling the EyeControl's Joystick [measured by successful correct performance of over 70% of the gestures].
 
○ Controlling the Rest mode and Siren mode [measured by successful correct performance of over 70% of the gestures].
 
○ Testing the logic of the pre-defined sentences; 
 
a. ability to say 10 pre-defined sentences [over 80% success rate];
 
 
 
 
 

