## 2 STUDY DESIGN

This will be a single center, single arm, open label, prospective study.

The study will be conducted in 2 enrollment stages. Initially, up to 10 healthy volunteers will be recruited and go through a short training for the use of the device followed by actual controlled use of several hours. In the second stage, up to 5 early stage ALS patients will be recruited and go through the same steps of training and device use.

Any feedback or safety concerns raised during the first stage of recruitment of healthy volunteers will be considered before moving forward to the second group of ALS patients.

The overall duration of participation for each subject will be up to 3 weeks.

The place: Rambam health care campus.

Each subject will go through a series of 4 meetings (2 meetings per week), and up to 3 hours per meeting. Meeting will be accompanied by company representatives and/or trained study team for support and guidance in each session..

Procedure will consist of an introduction and demonstration of the device features followed by actual use of the device by each subject (including control of gestures, use of menus, activation of pre- defined modes and writing full sentences). User feedback/questionnaire will be completed after the 2nd and 4th session.

The user's ability to perform each of the pre-defined tasks will be measured in each session. In addition, success rate and measured time for completion of pre-defined tasks, collected after the 4th session, will be compared to the success rate and times collected in previous sessions.

For detailed study procedures refer to section 4, as well as appendix A.

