### 4.3 VISIT 2 (PROCEDURE DAY/ MEETING #2)

**Second meeting** – will be performed at the clinic on the same week as the 1st meeting occurred (2-3 days post 1st meeting). (Each meeting will take about 2.5 hours):

1. **Refreshing about controlling the EyeControl's Joystick- ~ 1 hour.**

The user will be asked to use the logic of the joystick - the user will be asked to perform the eye gestures of: left, right, up, down and blink **-10 times for each gesture (total: 50 gestures)**. A computer with a visual software feedback will be attached to the user in order to assess and present the user results. The eye movement will be recorded in this stage, without recording the subject's face. The user will also be asked to turn on the Siren and rest modes.

2. **Testing the logic of the pre-defined sentences - ~ 1 hour.**

The first 20 min of the meeting will be dedicated for a short re-training on the logic of the device and the pre- defined sentences. Once completed, the user will be asked to perform specific gestures to complete **10 pre-defined sentences**.

The participant will also be asked to complete a usability and feedback questionnaire at the end of meeting #2.

3. Any adverse events will be recorded.

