#### **5.4 MANUFACTURING, SUPPLY AND SUPPORT OF DEVICE**

The EyeControl device is manufactured by Eyefree assistive communication Ltd. (Ramat Gan, Israel).

The device is supplied packed in a box that will be brought by the company.

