**10.5 PERSONAL DATA PROTECTION**

The Sponsor complies with the principle of subject's right to protection against invasion of privacy. Throughout this trial, all data will be identified only by an identification number and subject initials. The data will be blinded in all data analyses. The subject must be informed and consent is required that authorized personnel of the Sponsor and/or designee (Study Monitor, Auditor, etc.) and relevant Health regulatory agency

will have direct access to personal medical data to assure a high quality standard of the study

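### The protocol lets subjects complete the usability questionnaire, a primary-endpoint measure, with the device's maker present, which could bias it towards approval

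*Protocol*

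**What the plan says.** Section 1.7 lists three kinds of measure under the primary feasibility endpoint: ability to perform the device features, training time or learning curve, and usability. The last is a "feedback (user experience) questionnaire completed by each user". The synopsis lists the same.

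On timing, section 4.3 says: "The participant will also be asked to complete a usability and feedback questionnaire at the end of meeting #2". Section 4.5 says: "The users will be asked to complete a usability and feedback questionnaire at the end of meeting #4", and allots about 1 hour to it. Appendix A marks the questionnaire on procedure days 2 and 4.

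On who is present, section 2 says: "Meeting will be accompanied by company representatives and/or trained study team for support and guidance in each session". The synopsis says: "Meetings will be accompanied by company representatives and/or trained study team". Section 5.4 identifies the company as the maker: "The EyeControl device is manufactured by Eyefree assistive communication Ltd".

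On design, section 2 says: "This will be a single center, single arm, open label, prospective study". On confidentiality, section 10.5 says that "all data will be identified only by an identification number and subject initials" and that data are blinded when analysed.

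**The concern.** A user-experience rating is sensitive to who is watching. Someone asked for an opinion of a product while its maker sits in the room, having perhaps just helped with its use, has a social reason to soften criticism. The other primary measures are task success, completion time, words per minute and changes in results between meetings. The questionnaire is the only one that consists purely of the subject's opinion, so it is the most exposed.

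At stake is the credibility of the usability result in the final report. To a lesser degree, so is the candour of what healthy volunteers say before ALS patients are enrolled, since section 2 has first-stage feedback considered before the second stage.

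**Working it through.** No figure in the protocol bears on this point. It gives no questionnaire scale, standard deviation, target score or threshold, so there is nothing to reproduce or recompute. The check is to read the relevant sections against each other.

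1. **Is the questionnaire a primary measure?** Yes, in section 1.7 and in the synopsis.

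2. **Is it completed within a meeting?** The synopsis and section 2 place it after the 2nd and 4th sessions, which could mean once the session is over. The visit sections are more specific. In 4.3 it falls at the end of meeting 2 and is listed before adverse events are recorded. In 4.5 it is item 2 of meeting 4, ahead of adverse-event recording and the exit form. On this reading it belongs to the meeting.

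3. **May the maker be present?** Yes. Section 2 allows company representatives, trained study team, or both, in each session, and gives their purpose as support and guidance. Section 5.4 confirms that the company manufactures the device. A session staffed only by the site also complies.

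4. **Does anything separate the rating from the maker?** No section has company staff leave, names who hands out or collects the form, or provides for private or sealed completion. Section 10.5 governs how data are labelled and analysed, not who is in the room. The data also carry initials. With up to 10 volunteers and up to 5 patients, a representative who attended the meetings could recognise a respondent.

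5. **What would a shift do?** Write the true mean rating as m and the average shift due to the maker's presence as b. With one arm and no comparator, the expected observed mean is m + b whatever the number of subjects. More subjects narrow the interval around m + b but do not move it back to m. If the meeting 2 and meeting 4 ratings were compared, b would cancel only if it were the same at both. The protocol does not fix who attends, so that cannot be assumed. The same holds for comparing volunteers with patients.

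6. **Is help with the form foreseeable?** Section 3.1 requires unaffected speech in the ALS group and says nothing of hand function, while section 1.1 describes progressive weakness. Some patients may need physical help, and nothing prevents a company representative from giving it.

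**The case against.** The case on the other side has several parts, and much of it limits the point.

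- **Presence is optional.** A reader might infer that subjects will in fact be watched by the people who built the device. The protocol does not say that. Its and/or wording leaves attendance open, and it does not describe the representatives as developers. This stands, so the point is about what is permitted.
- **The bias is not shown.** Its direction is the expected one, but the document offers no evidence that it exists or how large it is. Any figure would need an assumed scale, spread and shift. This stands, and none is given here.
- **Contact time is not coaching time.** A reader might add up the session lengths and treat the total as coaching by the maker. That total would include the questionnaire hour at meeting 4 and much testing, and the coaching may come from site staff.
- **No criterion can be falsely met.** Other primary measures have thresholds (70%, 80%, under 2 minutes), but the questionnaire has none. Section 9 disclaims statistical significance and power. This stands.
- **Questionnaire scores do not decide stage 2.** A reader might infer that they do. Section 2 says only that feedback and safety concerns will be considered. It sets no rule and does not mention scores.
- **Section 10.5 already protects the data.** It does so for identification and analysis, but it leaves the setting in which the answer is given untouched.
- **Company contact has value in a first-in-human usability study.** True, but developers can hear comments during the rest of each session.

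It cannot be said that the matter belongs in a statistical analysis plan. Who is present when an outcome is collected is a matter of conduct, and no analysis can remove the effect afterwards.

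**Conclusion.** The point holds in a limited form. The protocol permits a subjective primary-endpoint measure to be collected in front of the device's maker, in a study with no comparator, and contains no safeguard at that step. This could bias the usability result towards approval. The size is unknown, and the consequence is confined to a descriptive summary that may be too favourable.

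The conclusion rests on two assumptions: that company representatives do attend at least some of meetings 2 and 4, and that their presence makes some subjects more generous. Neither is established by the document, and the first is left open by it. The protocol contains no internal contradiction or wrong figure here. The change is worth making because it removes an avoidable doubt at almost no cost.

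**What to change.** Add a sentence to each of sections 4.3 and 4.5 stating that:

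- company representatives leave the room before the questionnaire is handed out;
- the subject completes it alone, or with physical help from site staff only;
- site staff collect it and pass it to the company in coded form.

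For the coding to add anything to section 10.5, the copy passed on would need to omit initials.

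The change needs no additional visit, staff or subjects. Company staff lose live feedback at that moment, and scores may come out slightly lower than they otherwise would.
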